10.1.1 Time Period for Collecting Adverse Events

Adverse events will be collected from the time of signed informed consent until completion of the EOT visit. SAEs will be reported through the end of the safety follow-up period.

Ongoing SAEs at the safety follow-up phone call that, in the opinion of the Investigator, are associated with the IMP, will be followed and reported as described in Section 11.2.

All SAEs that, in the opinion of the Investigator, are associated with the IMP will be followed to resolution.

In the event a subject misses 5 consecutive weeks' worth of visits, they will be considered to have ceased treatment and withdrawn from the study. Investigators or designees must make a reasonable effort to contact the subject. Two documented attempts (e.g., phone, email, etc.) to contact the subject followed by a certified mailed letter is considered reasonable. Subjects who can no longer be contacted will be considered lost to follow-up.

10.1.2 Assessment of Intensity

The term "severe" is used to describe the intensity (severity) of a specific event (as in mild, moderate, or severe); the event itself, however, may be of relatively minor medical significance (such as a severe headache). This is not the same as "serious," which is based on subject/event outcome or action criteria usually associated with events that pose a threat to a subject's life or functioning. Seriousness (not severity) serves as a guide for defining regulatory reporting obligations.

Intensity	Definition
Mild	Causes transient or mild discomfort; no limitation of usual activities; no medical intervention required
Moderate	Causes mild to moderate limitation in activity; some limitation of usual activities; no or minimal medical intervention or therapy is required.
Severe	Causes marked limitation in activity; some assistance is usually required; medical intervention or therapy is required; hospitalization is probable.

Adverse events with changes in severity should be documented as separate events.

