The study will assess subjects that receive acute administration of SUBOXONE sublingual film followed by SUBLOCADE administration in the 1) ED, 2) inpatient unit or 3) within 7

days (168 h) after OD in an affiliated outpatient treatment clinic combined with 6 months of treatment with SUBLOCADE in the outpatient treatment clinic compared to historical and concurrent control data from VCU electronic health records. The affiliated clinic will agree to see the subject on arrival at the clinic during normal clinic hours.

Subjects will be given the opportunity to participate in an optional pharmacogenetics (PGx) sub-study.

- 1) Patients presenting to the ED for an opioid OD who received treatment with an opioid antagonist and are considered clinically stable and alert (respiratory rate [RR] \geq 12, pulse oximetry $>$ 95%, Glasgow Coma Scale [GCS] score of 15), and, who deny recent/regular use of long acting opioids (e.g., methadone) will be approached regarding interest in study participation. Written informed consent will only be obtained if the patient's judgement is intact as determined clinically by the Investigator or a medically qualified sub-investigator or research nurse. This OD will be considered the index OD.

Participants who meet inclusion/exclusion criteria will be administered 4 mg/1 mg SUBOXONE sublingual film in the ED followed by a 1-hour wait. If the subject displays no allergic/hypersensitivity reaction to SUBOXONE sublingual film after 1 hour, SUBLOCADE (300 mg) will be administered in the ED. Subjects will remain in the ED for 1 hour after the 300 mg SUBLOCADE injection and are clinically stable (respiratory rate [RR] \geq 12, pulse oximetry $>$ 95%, Glasgow Coma Scale [GCS] score of 15). A COWS assessment and AEs will be collected prior to SUBLOCADE administration and 1-hour post SUBLOCADE prior to discharge. Participants with initial COWS $<$ 8 and who were released from a controlled environment within the past 30 days, will remain in the ED for 2 hours after SUBLOCADE to assess for sedation using the Richmond Agitation-Sedation Scale. Patients will be discharged if RAS is 0 or greater. Patients who present with abnormal vital signs, or sign of sedation will remain in ED until they meet the ED discharge criteria. If participants experience precipitated withdrawal they will be treated symptomatically with medication as described in section 8.4 below.

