10 ADVERSE EVENTS

The Investigator or designee is responsible for identifying, documenting and reporting events that meet the definition of an AE.

An AE is any untoward medical occurrence in a subject associated with the use of an IMP regardless of the presence of a causal relationship to the IMP. An AE can be any unfavourable and unintended sign (including an abnormal laboratory finding) symptom or disease (new or exacerbated) temporally associated with an IMP, whether or not considered related to the IMP.

Events meeting the definition of an AE include:

- New condition detected after IMP administration even though the AE may have been present prior to receiving IMP.
- Exacerbation of a pre-existing condition (including intensification of a condition and/or an increase in frequency).
- Any abnormal laboratory test results or other safety assessments felt to be clinically significant in the opinion of the Investigator (including those that worsen from baseline).
- Symptoms and/or the clinical sequelae of a suspected interaction or an OD of either IMP or a concomitant medication.
- Signs, symptoms or the clinical sequelae resulting from special interest conditions (e.g., medication error, IMP withdrawal, injection site tampering resulting in removal of the depot etc.). Overdose per se will not be reported as an AE/SAE unless this is an intentional OD taken with possible suicidal/self-harming intent. This should be reported regardless of sequelae.
- Symptoms and/or clinical sequelae resulting from lack of efficacy will be reported if they fulfil the definition of an AE.
- Symptoms and/or clinical sequelae that resulted in intervention.

Events that do not meet the definition of an AE include:

- The disease/disorder being studied, or expected progression, signs, or symptoms of the disease being studied, unless more severe than expected for the subject's condition.
- Medical or surgical procedures; the condition that leads to the procedure is an AE.
- Situations where an untoward medical occurrence did not occur (e.g., social and/or convenience admission to a hospital, hospitalization for elective surgery, hospitalization for observation in the absence of an AE).
- Anticipated day-to-day fluctuations of pre-existing disease(s) or condition(s) present or detected at the start of the study that do not worsen.

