10.1 Assessment of Adverse Events

The Investigator is ultimately responsible for assessing and reporting all Aes as outlined in the protocol. The assessment and reporting of Aes may be delegated to a medically qualified sub-investigator, trained on this study protocol, who is listed on the delegation of authority log. All Aes regardless of treatment group or suspected causal relationship to the IMP will be reported as described in this protocol.

Adverse events should be volunteered by the subject or solicited from the subject using a standard statement, obtained from examination of the subject at a site visit, or from observations of clinically significant laboratory values or special examination abnormal values. If an event assessed by one of the study scales requires intervention, or if in the opinion of the Investigator, it is clinically significant, then it will be reported as an AE.

All Aes are to be assessed and recorded in a timely manner and followed to resolution or until the Investigator determines that there is not an anticipated resolution. Each AE is to be documented with reference to severity, date of occurrence, duration, treatment and outcome. Furthermore, each AE is to be classified as being serious or non-serious. In addition, the Investigator must assess whether the AE is IMP-related or not.

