14.9.1 Adverse Events

All AEs will be coded using MedDRA, summarized by treatment arm and reported to FDA. Adverse events that begin prior to SUBLOCADE administration or after the 6 month visit will be presented separately. Only AEs occurring after SUBLOCADE administration will be included in the analysis.

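### The AE analysis rule does not require an event to be new or worse after SUBLOCADE, so an AE that began before the injection and then eased can be analysed as a post-SUBLOCADE AE

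*Combined protocol and SAP*

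**What the plan says.** Five provisions of the combined protocol and SAP bear on this.

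- **Recording.** Section 10.1.2 says: "Adverse events with changes in severity should be documented as separate events". It does not limit this to increases in severity.
- **Content of a record.** Section 10.1 says: "Each AE is to be documented with reference to severity, date of occurrence, duration, treatment and outcome". A separate event therefore has its own severity and its own date.
- **Collection period.** Section 10.1.1 says: "Adverse events will be collected from the time of signed informed consent until completion of the EOT visit". For the ED route, the synopsis adds: "A COWS assessment and AEs will be collected prior to SUBLOCADE administration and 1-hour post SUBLOCADE prior to discharge". It has equivalent sentences for the inpatient and clinic routes. Appendix 1 schedules AE assessment before the SUBOXONE film, after the film and after SUBLOCADE.
- **Analysis.** Section 14.9.1 says: "Adverse events that begin prior to SUBLOCADE administration or after the 6 month visit will be presented separately". It continues: "Only AEs occurring after SUBLOCADE administration will be included in the analysis".
- **What counts as an AE.** Section 10 lists exacerbation of a pre-existing condition as an AE. Among events that are not AEs it lists: "Anticipated day-to-day fluctuations of pre-existing disease(s) or condition(s) present or detected at the start of the study that do not worsen". It also excludes expected signs and symptoms of the disorder under study, unless they are more severe than expected.

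The plan does not define a treatment-emergent AE, and it has no rule for linking or collapsing records that were split on severity.

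**The concern.** Every subject receives a SUBOXONE film and waits 1 hour before the SUBLOCADE injection. An AE that starts after the film can still be present at the injection, and AEs are assessed on both sides of it. If such an AE eases without resolving, section 10.1.2 opens a second record. Nothing in section 14.9.1 keeps that record out of the SUBLOCADE analysis, although the symptom predates the injection and got better.

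What is at stake is attribution. A film-related symptom could be reported as an event arising after the depot. The controls are anonymized health records (sections 6.1 and 13.1.1), so there is no parallel arm with AE data in which the artefact would also appear and could be recognised.

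**Working it through.** The plan gives no AE rate, so there is no figure to reproduce. The check applies the written rules to example records.

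**Step 1: apply the rules case by case.**

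- *Case A.* Nausea starts after the film, is moderate, and is mild 1 hour after SUBLOCADE. It was not present at study start, so the exclusion for pre-existing conditions does not reach it. Section 10.1.2 makes the mild phase a separate event, and section 10.1 gives that event its own date. If that date is the date of the change, the event falls after SUBLOCADE and is analysed. Analysed AEs: 1. Under a new-or-worsened rule: 0.
- *Case B.* An expected withdrawal symptom is present at study start and eases after the injection. Section 10 says it is not an AE, so section 10.1.2 never applies. Analysed AEs: 0 under either rule.
- *Case C.* An AE that began after the film becomes more severe after the injection. The worsened record is analysed under the literal reading and under a new-or-worsened rule. Analysed AEs: 1 under either.
- *Case D.* An AE that began after the film is mild and then resolves. Resolution opens no new record. Analysed AEs: 0 under either rule.

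The rules differ only in Case A: an AE above mild, first recorded between consent and injection, that eases without resolving.

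**Step 2: can Case A arise?** Yes. The synopsis plans evaluation of withdrawal symptoms that start or worsen after SUBOXONE and after SUBLOCADE. Section 10 counts symptoms that led to intervention as AEs, and section 8.4 lists symptomatic treatments for precipitated withdrawal. A symptom that appears after the film, is treated and then eases fits Case A.

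**Step 3: effect on the at-least-one-AE proportion.** Enrolment is about 100 (section 5.1). If k subjects have Case A and no other analysed AE, the proportion rises by k/100. For k = 1, 5 and 10 (assumed values), that is 1, 5 and 10 percentage points.

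**Step 4: what k might be, on assumptions only.** Let T be the share with a genuinely new or worsened AE, P the share with a qualifying AE ongoing at injection, and I the share of those whose AE eases before it resolves. If these are independent, inflation = (1 − T) × P × I. None of the three is in the documents. Assumed ranges: T 50% to 70%, P 5% to 20%, I 30% to 60%.

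- Low end: (1 − 0.70) × 0.05 × 0.30 = 0.0045, about 0.5 percentage points.
- High end: (1 − 0.50) × 0.20 × 0.60 = 0.06, 6 percentage points.

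The high end needs all three inputs at their extreme. I is 0 for mild AEs. If subjects with symptoms at injection are also likelier to have another AE during treatment, the inflation is smaller than the formula gives.

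**The case against.** **The mechanism is inferred.** The documents do not say that a split record takes the date of the severity change as its onset. Section 14.9.1 presents AEs that begin before SUBLOCADE separately, and nausea that began after the film did begin before SUBLOCADE. The data management plan cited in section 13.1 is not among the documents and may settle this. The objection stands as far as it goes: the misclassification is permitted, not prescribed. But no reading repairs the rule:

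- If a split record keeps its own date, Case A enters the analysis.
- If it inherits the earlier onset, Case A drops out, but so does Case C, a real worsening after SUBLOCADE.
- If occurring after SUBLOCADE includes AEs still ongoing, AEs that began earlier enter too, against the preceding sentence.

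**The named safety measure is wider.** Section 3.4 counts AEs at any time in the treatment period, and Appendix 1 places the film inside that period. On that wording nausea after the film counts already, and a split record adds nothing to the subject-level proportion. This is fair, but section 14.9.1 is the analysis rule and is narrower, so the two need to agree.

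**The consequences are limited.** Safety analysis is descriptive (section 14.9). No test or stopping rule depends on these counts, and records can be collapsed afterwards without loss. This stands and limits the weight of the point.

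**Stronger readings a reader might infer, which the documents do not support:**

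- *That every symptom present before the dose becomes a post-SUBLOCADE AE.* Section 10 removes expected disease symptoms and non-worsening conditions present at study start. Section 1.1.2 expects significant withdrawal before dosing, so many early symptoms would be excluded. Clinic entrants may also present up to 7 days after the overdose.
- *That a headache going from mild to severe to mild inflates the safety measures threefold.* It makes three records but remains one subject with an AE. The measures in section 3.4 are proportions of subjects, and no analysis of total events or AE duration is specified.
- *That the drug-related proportion is inflated.* Section 10.1.3 requires a causality judgement for each AE. A new record is not automatically related.

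**Conclusion.** The point holds in a narrow form. Two written rules, a severity split in either direction and selection by timing alone, together allow an AE that began between consent and injection, then eased, to be analysed as a post-SUBLOCADE AE. This rests on reading the split record as dated at the severity change. That is the natural reading of sections 10.1 and 10.1.2 together, but it is not stated.

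The effect is confined to descriptive AE incidence by term, and to the at-least-one-AE proportion for subjects with no other AE. Its size cannot be derived from the documents and is probably small. The range of about 0.5 to 6 percentage points is an illustration on assumed inputs, not an estimate. A reader might reach 15 points with P = 50%, T = 50% and I = 60% (0.50 × 0.50 × 0.60 = 0.15), but nothing in the documents supports so large a P once the section 10 exclusions apply.

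The efficacy analyses are unaffected. The change is still worth making, because the present rule can credit film-related symptoms to the depot and the remedy costs almost nothing.

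**What to change.** Amend section 14.9.1 to say that:

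1. an AE is analysed if it first begins, or increases in severity, after the first SUBLOCADE injection;
2. a decrease in severity does not create a new analysed event;
3. each subject is counted once per preferred term, at maximum severity;
4. AEs that began before the first injection and did not worsen are listed separately.

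The recording rule in section 10.1.2 can stay, provided that split records are linked, or are collapsed at analysis by term and contiguous dates. A cross-reference from section 3.4 would settle which window its proportions use.

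The cost is a few sentences and minor programming. No additional data need be collected, and records already entered can be handled the same way. The reported AE count may be slightly lower than under the present wording.

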10.1.3 Assessment of Causality

The Investigator or a medically qualified sub-investigator, trained on this study protocol, listed on the delegation of authority log is responsible for determining the AE relationship to the IMP.

The following categories will be used to define the relationship of an AE to the administration of the IMP:

- Not Related: Data are available to identify a clear alternative cause for the AE other than the IMP.
- Related: The cause of the AE is related to the IMP and cannot be reasonably explained by other factors (e.g., the subject's clinical state, concomitant therapy, and/or other interventions).

A "reasonable possibility" is meant to convey that there are facts/evidence or arguments to suggest a causal relationship, rather than a relationship cannot be ruled out. The Investigator will use clinical judgment to determine the relationship. Alternative causes, such as natural history of the underlying diseases, concomitant therapy, other risk factors and the temporal relationship of the event to the IMP will be considered and investigated. The Investigator will also consult the IB and/or USPI, for marketed products, in the determination of his/her assessment. For each AE/SAE the Investigator must document in the medical notes that he/she has reviewed the AE/SAE and has provided an assessment of causality.

There may be situations when an SAE has occurred and the Investigator has minimal information to include in the initial report. However, it is imperative that the Investigator always make an assessment of causality for every event prior to the initial transmission of the SAE data to Indivior or designated representative. The Investigator may change his/her opinion of causality in light of follow-up information and amend the SAE data collection tool accordingly. The causality assessment is one of the criteria used when determining regulatory reporting requirements.

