11.2.2 Regulatory Reporting Requirements for Serious Adverse Events

Prompt receipt of notifications of SAEs to the IRB or designated representative from investigators is essential in ensuring that legal obligations and ethical responsibilities regarding the safety of subjects are met.

A suspected unexpected serious adverse reaction (SUSAR) is an SAE related to the IMP administered in any dose and that, in its nature or severity, is inconsistent with the IB or Product Information for marketed products.

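### The two causality categories in Section 10.1.3 leave a gap and do not match the section's own 'reasonable possibility' standard, so drug-related AE counts and the 'related' limb of SUSAR identification may be classified inconsistently

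*Combined protocol and SAP*

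**What the plan says.** Section 10.1 asks for a binary answer: "the Investigator must assess whether the AE is IMP-related or not". Section 10.1.3 supplies the two categories.

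- Related is defined as "The cause of the AE is related to the IMP and cannot be reasonably explained by other factors". The examples of other factors are the subject's clinical state, concomitant therapy and other interventions.
- Not Related is defined as "Data are available to identify a clear alternative cause for the AE other than the IMP".

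The next paragraph of the section explains the term 'reasonable possibility' as meaning that "there are facts/evidence or arguments to suggest a causal relationship, rather than a relationship cannot be ruled out". The term appears in neither category. The same paragraph states that "The Investigator will use clinical judgment to determine the relationship", and lists alternative causes and timing among the things to be considered. An assessment must be made for every SAE before it is first transmitted, and "The causality assessment is one of the criteria used when determining regulatory reporting requirements".

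The classification is used in Section 3.4 (proportions with a drug-related AE and with a serious and drug-related AE) and in Section 11.2.2: "A suspected unexpected serious adverse reaction (SUSAR) is an SAE related to the IMP administered in any dose". Two other places use different terms for a causal link. Section 10.1.1 says "All SAEs that, in the opinion of the Investigator, are associated with the IMP will be followed to resolution", and Section 12.1 speaks of SAEs in pregnancy that are possibly related to study treatment.

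**The concern.** A binary classification works only if its two definitions cover every case. Here each category has its own positive requirement, and the two requirements are not complements. An investigator who has a plausible drug effect and a reasonable competing explanation has no category that fits.

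The situation should be common in this trial. Section 1.1.2 expects subjects to be in significant withdrawal after an opioid antagonist, and Section 1.2 names precipitated withdrawal as a risk of the study drug. Section 1.1.3 lists raised hepatic enzymes as a common reaction, while the synopsis advises acetaminophen as needed at discharge and Appendix 3 investigates viral hepatitis and acetaminophen as causes of liver injury. Because concomitant therapy counts against Related, the categories also have no place for joint causation.

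At stake are the two causality-based proportions in Section 3.4 and the first of the two conditions for a SUSAR. The study is open-label without a randomised comparator, and the documents describe no AE collection in the controls, whose data are an anonymised record extract (Section 13.1.1). Investigator attribution is therefore the main means of separating drug effects from background events.

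**Working it through.** No sample size, power or event count is involved, and the plan states no figure to reproduce. The check is logical: list the evidence an investigator may hold, test it against each definition, then trace where the answer is used.

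**Step 1. Evidence states against the two definitions in Section 10.1.3.**

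1. A clear alternative cause is shown by data. Not Related is met; Related is not.
2. The drug is judged to be the cause and no other factor reasonably explains the event. Related is met; Not Related is not.
3. There is a reasonable but unproven alternative, and the drug is also plausible. Related fails because another factor can reasonably explain the event. Not Related fails because no clear alternative has been identified. Neither is met.
4. There is no clear or reasonable alternative, but the drug is not established as the cause. Related fails on its first condition; Not Related fails for want of an alternative. Neither is met.

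The categories do not overlap, but 2 of the 4 states are unassigned. This counts types of evidence, not events.

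**Step 2. The 'reasonable possibility' sentence.** Take state 3, with facts or arguments pointing to the drug. The event meets the standard that the section explains, yet fails the category Related. So the section holds two different thresholds, and the more inclusive one is attached to no category.

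**Step 3. Uses that depend on the category.**

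- Section 3.4 lists five AE proportions: any AE, drug-related AE, SAE, serious and drug-related AE, and AE leading to discontinuation. The second and fourth depend on causality: 2 of 5.
- Section 11.2.2 makes a SUSAR an SAE that is both related and inconsistent with the Investigator's Brochure or product information. The first condition depends on the category; the second does not.

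**Step 4. Uses that do not depend on it.**

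- Section 10.1: all AEs are reported whatever the suspected causality, and all are followed until they resolve or the investigator expects no resolution.
- Section 11.2.1: all SAEs go to the IRB and to the company supplying the drug within 24 hours.
- Section 14.9.1: all AEs are coded, summarised and reported to FDA.
- Section 10.1.1: SAEs are reported through the safety follow-up period. The extra follow-up rule there rests on the investigator's opinion that an SAE is associated with the drug, a term not tied to Related.

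**Step 5. Direction.** A state 3 event called Not Related lowers the drug-related proportion; called Related, it raises it. Each choice breaks one of the two definitions, so the text does not fix the direction. The documents give no frequency for states 3 and 4, so no misclassification rate can be derived.

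**The case against.** The strongest reply is that Section 10.1.3 leaves the decision to clinical judgment, asks the investigator to weigh timing and to consult the Investigator's Brochure or prescribing information, and bars Related only where another factor reasonably explains the event. A listed reaction with consistent timing need not be called Not Related because an alternative exists in theory. The safety summaries are descriptive (Section 14.9), and no efficacy result changes.

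Much of this stands, and it limits the point. It does not close the gap. Judgment applies the definitions but cannot supply a missing one, and the assessment may be delegated to sub-investigators, so two trained assessors could follow the text and label the same event differently.

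The documents do not support several stronger readings that a reader might infer.

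- *That drug-related events are systematically under-counted, because any conceivable alternative defeats Related.* The text says reasonably explained, and events in the gap fail Not Related as well. Understatement is possible but not shown.
- *That events are lost or not followed.* Sections 10.1, 11.2.1 and 14.9.1 apply whatever the causality. Only the label is at risk.
- *That a serious sedation or respiratory event with benzodiazepines shows a missed SUSAR.* Section 9.6.2 already names respiratory depression, profound sedation, coma and death as risks of that combination and points to the prescribing information. Such an event would probably fail the unexpectedness condition however causality is rated. It bears on the serious and drug-related count instead.
- *That most known reactions would be barred.* Section 1.1.3 names 8 common reactions, 2 of them at the injection site, leaving 8 − 2 = 6 for which an alternative can be imagined. That is a count of names, not a misclassification rate. An alternative must be reasonable for the individual subject and time, and exclusion criteria 14, 15 and 17 (intoxication, severe alcohol or benzodiazepine use disorder, raised liver tests) remove some alternatives at entry.

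**Conclusion.** The point holds as a defect in the definitions. The categories in Section 10.1.3 are not exhaustive, and they conflict with the section's own 'reasonable possibility' sentence: an event can meet that standard and still fail Related. The firm consequence is exposure to inconsistent classification in two of the five AE proportions in Section 3.4 and in the 'related' limb of SUSAR identification. Understatement is a possible further consequence.

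The size is unknown, because the documents give no rate of events in the gap. The conclusion assumes that assessors apply the definitions as written and have no further guidance, for example in eCRF completion instructions that are not part of these documents. Sample size, power and the efficacy analyses are untouched.

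**What to change.** Redraft the two categories in Section 10.1.3 around the standard the section already contains.

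- Related: there is a reasonable possibility, in the section's sense of facts, evidence or arguments, that the study drug caused or contributed to the AE, including when other factors may also have contributed.
- Not Related: there is no such reasonable possibility.
- Delete the second condition of the present Related definition, the one on explanation by other factors.
- Use the same standard and term in Section 10.1.1 (now associated with the drug) and Section 12.1 (now possibly related).

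Every evidence state then has a category. States 3 and 4 become Related where facts or arguments point to the drug, and Not Related otherwise.

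The cost is a few sentences in the protocol and the eCRF completion guide. The reported drug-related AE rate may be higher than under the present wording. Treatment, visits and sample size do not change.
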